13.1 Definitions

Unanticipated Problems Involving Risk to Subjects or Others (UPIRTSO)

Any unanticipated problem or adverse event that meets the following three criteria:

- Serious: Serious problems or events that results in significant harm, (which may be physical, psychological, financial, social, economic, or legal) or increased risk for the subject or others (including individuals who are not research subjects). These include: (1) death; (2) life threatening adverse experience; (3) hospitalization - inpatient, new, or prolonged; (4) disability/incapacity - persistent or significant; (5) birth defect/anomaly; (6) breach of confidentiality and (7) other problems, events, or new information (i.e. publications, interim findings, product labeling change) that in the opinion of the local investigator may adversely affect the rights, safety, or welfare of the subjects or others, or substantially compromise the research data, **AND**
- Unanticipated: (i.e. unexpected) problems or events are those that are not already described as potential risks in the protocol, and consent document, or not part of an underlying disease. A problem or event is "unanticipated" when it was unforeseeable at the time of its occurrence. A problem or event is "unanticipated" when it occurs at an increased frequency or at an increased severity than expected, **AND**

- Related: A problem or event is "related" if it is possibly related to the research procedures.

- Unanticipated Adverse Device Effect:

Any serious adverse effect on health or safety or any life-threatening problem or death caused by, or associated with, a device, if that effect, problem, or death was not previously identified in nature, severity, or degree of incidence in the investigational plan or application (including a supplementary plan or application), or any other unanticipated serious problem associated with a device that relates to the rights, safety, or welfare of subjects. In the event of attempted device implant with circumstances that prevent implant due to malfunction or deficiency the unused devices will be retained until arrangements for its collection are made and can be returned to Neovasc for further analysis and investigation.

There are several inherent risks associated with this protocol that must be considered. There are risks associated with the various study procedures including cardiac catheterization, CS Reducer implantation, invasive coronary reactivity testing, and exercise testing.

Contemporary overall rates of major complications (death/ myocardial infarction/ stroke/ unplanned coronary bypass grafting/ pericardial effusion) related to diagnostic cardiac catheterization procedures at our institution are extremely low (<1 per 1000 left heart catheterization)⁴⁹. Second, coronary reactivity testing is a safe procedure with <1/100 risk of severe adverse events (coronary artery dissection and myocardial infarction)⁵⁰. Third, in the largest available database (REDUCE study), CS Reducer implantation procedure was also shown to be a safe procedure with no CS perforations, cardiac tamponade, peri-procedural

death or myocardial infarction reported in the largest database available at 14 months median follow-up ⁴¹. Lastly, exercise testing may pose a minimal risk to patients if they were to develop arrhythmias during the testing. This risk is minimal, and the room in which EBEST is performed, and personnel performing testing will be equipped to handle any potential complications.

13.2 Adverse Event

An adverse event will be defined as any medical occurrence in a subject or clinical investigation subject that is temporally associated with use of the medicinal product, whether or not it is considered related to the medicinal product. This is thus any unfavorable or unintended sign, such as abnormal symptoms, laboratory values, or new disease, which can be associated with the CS Reducer implantation by temporal association.

13.3 Serious Adverse Event

Adverse events are classified as serious or non-serious. Serious problems/events can be well defined and include;

- Death
- Myocardial infarction
- Stroke
- Life threatening adverse procedural or periprocedural complications
- Any hospitalizations post CS Reducer implantation
- Inpatient, new, or prolonged; disability/incapacity

and/or per protocol may be problems/events that in the opinion of the sponsor-investigator may have adversely affected the rights, safety, or welfare of the subjects or others, or substantially compromised the research data. Serious adverse events are ones that may result in death or can be life-threatening, requires extended hospitalization, significant disability, meaning a substantial disruption to the person's ability to conduct normal life functions. This excludes experiences of minor medical significance such as headache, nausea, vomiting, influenza, diarrhea, accidental trauma, which may disrupt daily functions but is not substantial. Medical or scientific judgment should be exercised when deciding whether reporting is appropriate in situations.

All adverse events that do not meet any of the criteria for serious, should be regarded as non-serious adverse events.

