Allergic reaction	0(0.00)	0(0.00)	0(0.00)

Arrhythmias (e.g. ventricular tachycardia (VT) or ventricular fibrillation (VF))	1(1.92)	4(1.96)	0(0.00)
Dissection (e.g. coronary sinus)	0(0.00)	4(1.96)	2(0.11)
Embolism (e.g. pulmonary or vessel)	0(0.00)	0(0.00)	0(0.00)
Conduction Disturbances	0(0.00)	0(0.00)	0(0.00)
Hypotension/hypertension	0(0.00)	0(0.00)	1(0.05)
Infection	0(0.00)	0(0.00)	0(0.00)
Access site complications	1(1.92)	1(0.49) ²	0(0.00)
Access site hematoma (not SAE)	Not reported	8(3.92)	Not reported
Access site minor bleed (not SAE)	Not reported	4(1.96)	Not reported
Ischemic events (e.g. myocardial infarction (MI) or unstable angina)	1(1.92)	0(0.00)	0(0.00)
Minor or major bleeding events (e.g. hemorrhage, cardiac tamponade, or pericardial effusion)	1(1.92)	1(0.49)	1(0.05)
Vascular event (e.g. pseudoaneurysm or thrombus)	0(0.00)	0(0.00)	0(0.00)
Perforation/rupture of coronary sinus, right atrium (RA), or internal jugular vein	0(0.00)	1(0.49)	3(0.16)
Pulmonary edema	0(0.00)	0(0.00)	0(0.00)
Reducer and/or coronary sinus occlusion (e.g. thrombus)	0(0.00)	0(0.00)	0(0.00)
Reducer fracture	0(0.00)	0(0.00)	0(0.00)
Reducer malposition, migration or embolization	2(3.85)	2(0.98)	10(0.54)
Respiratory failure	0(0.00)	0(0.00)	0(0.00)
Spasm of CS or jugular vein	0(0.00)	0(0.00)	0(0.00)
Cardiac valve injury (tricuspid)	0(0.00)	0(0.00)	0(0.00)
Myocardial damage	0(0.00)	0(0.00)	0(0.00)
Pyrogenic immunological or toxicological reaction	0(0.00)	0(0.00)	0(0.00)
Angina	0(0.00)	3(1.47)	0(0.00)
Chest pain ¹	1(1.92)	1(0.49)	0(0.00)

Minor neurologic event, including dysphagia, blurred vision, or TIA	0(0.00)	3(1.47)	0(0.00)
---	---------	---------	---------

¹*Chest pain has previously been categorized as angina and is therefore not currently included as an independent complication in the IFU*

²*Access Site Complications: one (1) access site complication due to device retrieval via the femoral vein*

³*Source: 022-CLN-012-2019 Rev A*

Table 2: Technical Success of CS Reducer Implantation Procedure

Study	N	Technical Success % (n)
COSIRA Treatment Arm	52	96.2 (50/52) ¹
FIM	15	93.3 (14/15) ²
REDUCER-I Overall	211	96.6 (204/211) ³
REDUCER-I Arm 1	161	95.6 (154/161) ³

¹ *Two subjects were not implanted – one due to inability to cannulate the CS and one due to inability to advance the guide catheter in the CS to the intended implant location*

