CS Reducer is being tested as an add-on therapy for ANOCA patients with microvascular dysfunction and ongoing refractory angina despite optimal tolerated conventional medical therapy. Any previously ongoing therapy for CMD or other conditions, prior to CS Reducer implantation, can be continued during the study.

11- Study Procedures

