13.5 Preexisting Condition

A preexisting condition is one that is present at the start of the study. A preexisting condition should be recorded as an adverse event if the frequency, intensity, or the character of the condition worsens during the study period.

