13.9 Hospitalization, Prolonged Hospitalization or Surgery

Any adverse event that results in hospitalization or prolonged hospitalization should be documented and reported as a serious adverse event unless specifically instructed otherwise in this protocol. Any condition responsible for surgery should be documented as an adverse event if the condition meets the criteria for an adverse event.

Neither the condition, hospitalization, prolonged hospitalization, nor surgery are reported as an adverse event in the following circumstances. Hospitalizations that do not necessitate reporting as adverse events, including those that are scheduled as a part of the study or as a part of the predetermined care of the patient, or hospitalization for preexisting conditions, including elective surgical procedures. These include:

- Hospitalization or prolonged hospitalization for diagnostic or elective surgical procedures for a preexisting condition. Surgery should not be reported as an outcome of an adverse event if the purpose of the surgery was elective or diagnostic and the outcome was uneventful.
- Hospitalization or prolonged hospitalization required to allow efficacy measurement for the study.

- Hospitalization or prolonged hospitalization for therapy of the target disease of the study, unless it is a worsening or increase in frequency of hospital admissions as judged by the clinical investigator.

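### Sections 13.3 and 13.9 can classify the same post-implant angina admission as an SAE or as no adverse event, and no section says which governs

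*Combined protocol and SAP*

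**What the plan says.** Section 13.3 includes "Any hospitalizations post CS Reducer implantation" in its list of serious events. It states no exception and does not refer to 13.9.

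Section 13.9 starts from a similar rule: an adverse event leading to admission "should be documented and reported as a serious adverse event unless specifically instructed otherwise in this protocol". It then sets out exemptions, introduced by "Neither the condition, hospitalization, prolonged hospitalization, nor surgery are reported as an adverse event in the following circumstances". One of them is "Hospitalization or prolonged hospitalization for therapy of the target disease of the study, unless it is a worsening or increase in frequency", and the sentence leaves that decision to one person: "increase in frequency of hospital admissions as judged by the clinical investigator".

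Section 10 identifies the disease: "CS Reducer is being tested as an add-on therapy for ANOCA patients with microvascular dysfunction and ongoing refractory angina". Admissions to treat angina therefore fall within the exemption.

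Two other provisions bear on the point. Section 13.5 states: "A preexisting condition should be recorded as an adverse event if the frequency, intensity, or the character of the condition worsens". The introduction to Section 13 requires investigators to notify the sponsor-investigator of every procedure or hospitalisation, so that events needing adjudication can be adjudicated.

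**The concern.** Whether an angina admission after implant is counted depends on which section the site follows. If it follows 13.9, the count depends on a judgement of worsening. The study is open label with a single arm (Section 6.1), and the judgement concerns the symptom that the CCS and SAQ endpoints are meant to show improving. It also acts as a filter at entry: an admission judged not to be a worsening is not an adverse event at all, so it does not reach a later step where relatedness could be assessed.

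These admissions cannot be presumed to be background disease. Table 1 in Section 3 lists angina, chest pain and ischaemic events among the potential complications of this device. Section 13.2 defines an adverse event by its timing, whether or not it is thought related. Filtering by presumed cause sits badly with that definition.

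At stake is the completeness of the serious-event record behind Aim 5.4 (safety) and behind the independent review for which 13.14 sets up the DSMB.

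**Working it through.** The plan gives no figure on this point to reproduce. The check is a comparison of text, followed by arithmetic for scale on assumed rates.

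**Step 1. One event under each reading.** Take a patient admitted on Day 50 for treatment of angina.

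| Section followed | Investigator judges worsening or more frequent admissions | Investigator does not |
|---|---|---|
| 13.3 | SAE | SAE |
| 13.9 | SAE (general rule applies) | Neither admission nor condition is reported as an AE |

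The readings differ only in the right-hand column. Section 13.5 does not close that gap, because it too needs a finding of worsening. Another 13.9 exemption, for admissions for diagnostic procedures in a pre-existing condition, carries no worsening safeguard. Angina pre-exists in every participant, so an admission to work up chest pain might be placed there.

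**Step 2. What uses the classification.**

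- AE/SAE tally: affected directly.
- Section 13.4, SAE form within 24 hours: affected, because it applies only to events classed as SAEs.
- Section 13.14, DSMB: affected, because its stated task is independent review of adverse events. An admission not recorded as one has no stated route to it. The notification in the Section 13 introduction goes to the sponsor-investigator.
- Section 7.4, 1 of 5 consecutive patients with serious adverse safety events: affected if that term, which is not defined, means 13.3 SAEs.
- Section 13.14, 3/5 stopping rule: counts only SAEs deemed secondary to the device, so affected only if the admission is so attributed.
- Section 6.3, procedural MACE: contains neither hospitalisation nor angina, so unaffected.

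**Step 3. Scale.** Let p be the per-patient probability of an angina admission by Day 120 that falls in the disputed cell. The documents do not give p, so 5%, 10% and 20% are assumptions. With n = 30 (Section 6.1), the expected number of patients is 30p, and the chance of at least one in a given five is 1 − (1 − p)^5.

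| Assumed p | 30p | 1 − (1 − p)^5 |
|---|---|---|
| 5% | 1.5 | 1 − 0.95^5 = 23% |
| 10% | 3 | 1 − 0.90^5 = 41% |
| 20% | 6 | 1 − 0.80^5 = 67% |

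Under 13.3 all of these patients count as SAEs; under 13.9 none need do so.

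Exact (Clopper-Pearson) 95% intervals show what reclassification does to a reported proportion if there are no other SAEs:

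- 0/30: 0% to 11.6%, the upper limit being 1 − 0.025^(1/30)
- 1/30 = 3.3%: 0.1% to 17.2%
- 3/30 = 10.0%: 2.1% to 26.5%

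The nearest document figures are the angina counts in Table 1: 0/52, 3/204 (1.47%) and 0/1840. At 1.47% the expected number is 30 × 3/204 = 0.44 patients. These are complication events, not admissions, so they neither support nor exclude the assumed rates.

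**The case against.** The best defence is that the sections are a rule and its exception. Section 13.3 opens by sorting adverse events into serious and non-serious, so its list may grade only events that already qualify as adverse events. It also calls for medical judgement on whether to report. Section 13.9 reserves exceptions given elsewhere in the protocol, and its bullets can be read as those exceptions. On that view only a cross-reference is missing.

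This reading is tenable, but 13.3 says any hospitalisation and nothing states the order of precedence. More importantly, if 13.9 does govern, the open-label filter becomes the intended rule, and the right-hand cell of the comparison stays uncounted.

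Several limits on the harm do stand. Two triggers in 13.9, and 13.5, bring worsened angina back into reporting. Myocardial infarction is a separate SAE item in 13.3. Undifferentiated chest pain is not automatically therapy of the target disease. Every hospitalisation is still notified to the sponsor-investigator, adverse events are asked about at each contact (13.10), and CCS class and SAQ are collected at Days 30, 60, 90 and 120. A reader might infer that angina admissions disappear from the study; the documents support only that they can go uncounted as AEs or SAEs.

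A reader might also infer that there is no baseline against which to judge more frequent admissions. Screening collects medical history (11.1) and the case report forms are not shown, so all that can be said is that no baseline admission count is specified.

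**Conclusion.** The point holds as a conflict between 13.3 and 13.9 with no stated precedence, which leaves the status of an angina admission to an unblinded judgement. It should be corrected, but it does not undermine the trial's main endpoints.

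Its size is unknown. If 5% to 20% of patients had such an admission without a finding of worsening, about 1.5 to 6 of 30 would be SAEs under one section and possibly none under the other. That rests wholly on the assumed rates.

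It is tempting to conclude that the safety result will be biased in the device's favour. The documents do not establish that. Section 12 plans no SAE-rate analysis, so 3/30 against 0/30 is an illustration and not a planned result. The pre-specified safety endpoint, procedural MACE, is untouched. A single admission could decide whether 7.4 is met only if the other four patients have no qualifying event and the term used there means 13.3 SAEs. What is shown is that the serious-event record can be incomplete in one direction, before independent review.

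**What to change.** 1. Reconcile 13.3 and 13.9, with a cross-reference stating which governs.
2. Confine the 13.9 exemption to admissions scheduled by the protocol or planned beforehand. Record every unplanned post-implant admission, including those for angina or chest pain, with the investigator's view of worsening and of relatedness entered as data fields instead of deciding whether the event is recorded.
3. Give the DSMB, and include in the final report, a listing of all post-implant hospitalisations by cause to Day 120, whatever their AE status.
4. State whether the serious events meant in 7.4 are those of 13.3.

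Other recording conventions could also work. The essentials are a stated precedence and a complete listing. The cost is a wording amendment, a few more forms in a 30-patient study, and possibly a slightly higher reported SAE count.

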13.4 Adverse Event Reporting Period

Serious adverse events should be reported using the Serious Adverse Event Report Form within 24 hours of study personnel becoming aware of an event. This data must be entered into the electronic capture system within 24 hours as well.

If serious adverse event results in death or is considered to be related to the study device, then the medical monitor must be contacted immediately.

The follow-up period is defined as 4 months following CS Reducer implant. This is the study period during which adverse events must be reported.

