² *One subject experienced a migration post-implantation. The Reducer was noted to have moved during insertion but was inflated. As a result, the position of the deployed Reducer device was more proximal than desired. The dislodged Reducer then migrated and a 2nd Reducer was implanted without complications*

³ *Seven subjects were not implanted – 2 for CS dissection, 2 for tortuous anatomy, 1 for CS too small, 1 for inability to advance the guiding catheter, and 1 for movement of the Reducer while retracting the guidewire*

Accordingly, in this Phase-1 study we aim to evaluate the feasibility of CS Reducer implantation and its efficacy on invasively assessed microvascular function in ANOCA patients with CMD.

4- Study Hypothesis

In patients with ANOCA and invasive evidence of CMD, CS Reducer implantation is safe and will improve microvascular function as measured by CFR and HMR.

5- Aims

- 5.1 To evaluate the potential efficacy of CS Reducer implantation in ANOCA patients with CMD on microvascular function using invasive CFR and HMR assessments
- 5.2 To evaluate the potential efficacy of CS Reducer implantation in ANOCA patients with CMD on angina severity and frequency as assessed by CCS angina class and short-acting nitrates use, ischemia and exercise capacity as assessed by exercise bike echocardiographic stress test (EBEST), and quality of life as assessed by SAQ score.
- 5.3 To evaluate the potential efficacy of CS Reducer on left ventricular diastolic function and filling pressures as assessed by transthoracic echocardiographic parameters at peak exercise
- 5.4 To confirm the safety and feasibility of CS Reducer implantation patients with ANOCA and invasively documented CMD.
- 5.5 A successful demonstration in the proposed trial that CS Reducer implantation can be beneficial to patients with CMD will significantly advance the field of research aimed at FDA approval of the CS Reducer for treatment of ANOCA patients with CMD and opening the door to commercialization of CS Reducer for treatment of CMD, which is a critical unmet clinical need. If successful, the next stage of investigation will be the conduct of one or more pivotal registration studies to support FDA approval, and the proposed trial will provide information necessary to design these studies.

6- Study design

6.1 General Study Design:

- Prospective, single center, open label, single arm, clinical trial
- Number of participants: 30 subjects
- Duration of study: 4 months

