The first six patients will be sequentially enrolled, and subsequent enrollment will be held until one-month follow-up. Provided there are no safety concerns at this time, enrollment will continue. Staggered enrollment will help ensure that subsequent patients are not enrolled until there is adequate follow-up and safety of initial patients. The patients for this study will be recruited through the outpatient clinics in the Department of cardiology, including the Chest Pain and Coronary Physiology Clinic and the Coronary Artery Disease Clinic at Mayo Clinic. There have been over 35,000 patients seen in the Cardiovascular Division at Mayo Clinic yearly. There are over 6,000 cardiac catheterizations performed yearly in the cardiac catheterization lab. As a part of our clinical practice, patients with angina referred to the catheterization laboratory for a clinically indicated coronary angiography and found to have non-obstructive CAD are undergoing a comprehensive coronary reactivity testing including assessment of microvascular function with CFR and HMR. Typically, 8-10 patients per month undergo this comprehensive coronary physiology study. This will be mediated through referring physicians. Patients that meet inclusion and exclusion criteria will be considered for recruitment in the study.

7.4 When and How to Withdraw Subjects:

Subjects will be withdrawn from the study prior to completion of all study related procedures if 1 of 5 consecutive patients have serious adverse safety events.

7.5 Data Collection and Follow-up for Withdrawn Subjects:

Even though a subject has withdrawn from the study, it may be important to collect some follow-up or survival data on such subjects throughout the protocol defined follow-up period. Such data is important to the integrity of the final study analysis since early withdrawal could be related to the safety profile of the study device and/or implantation procedure. If a subject withdraws consent to participate in the study, for subject safety reasons, we will make attempts to obtain permission to collect follow up information whenever possible.

[figure not shown]

Figure 3: Flow chart of the study design. CAD: coronary artery disease; CMD: coronary microvascular dysfunction; CRT: coronary reactivity testing; CFR: coronary flow reserve; HMR: Hyperemic microvascular resistance; CCS: Canadian cardiovascular society; SAQ: Seattle angina questionnaire; EBEST: Exercise bike echocardiographic stress test.

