The investigator will be responsible for the detection and documentation of any adverse events or serious adverse events as defined by this protocol. During the study there will be several safety evaluations and the investigator and/or site staff will be responsible for

detecting, documenting and reporting both adverse events and serious adverse events as defined by this protocol. These will be reported from the signing of the informed consent through the 4-month visit. Serious adverse events will be reported from the signing of the informed consent through the 4 month visit as well. Investigators will report any procedure or hospitalization to the Sponsor-Investigator to ensure any event needing adjudication can be done so in a timely fashion.

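### Follow-up contacts are timed from implant, and the plan gives no Day 0 or scheduled contacts to a patient whose implantation is attempted but fails.

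*Combined protocol and SAP*

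**What the plan says.** Section 13.4 sets the clock: "The follow-up period is defined as 4 months following CS Reducer implant". It adds: "This is the study period during which adverse events must be reported". The calls in Sections 11.4–11.6, the final visit in Section 11.7 and the matching columns of the schedule in Section 11.8 are all labelled post-implant.

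The opening of Section 13 gives a different window for adverse events: "These will be reported from the signing of the informed consent through the 4-month visit". For serious events it says: "Serious adverse events will be reported from the signing of the informed consent through the 4 month visit as well". That window opens at consent, but it closes at a visit that is itself counted from implant.

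The one sentence about a failed attempt in this trial is in Section 13.1: "In the event of attempted device implant with circumstances that prevent implant due to malfunction or deficiency the unused devices will be retained". It concerns the device, not the patient, and only malfunction or deficiency.

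Section 13.3 lists among serious events: "Any hospitalizations post CS Reducer implantation". Section 13.9 treats any adverse event leading to hospitalisation as serious, apart from listed planned or pre-existing reasons, and sets no implant condition.

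Section 7.5, on withdrawn subjects, says: "it may be important to collect some follow-up or survival data on such subjects". It goes on to call such data important to the final analysis and commits to seeking permission to collect it.

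Section 12 restricts the analysis to patients who completed every procedure and all follow-up.

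**The concern.** A patient can have venous access and coronary sinus instrumentation and leave without a device. The protocol's own evidence shows that this happens, and that some attempts end because of a complication. Footnote 3 to Table 2 reads: "Seven subjects were not implanted – 2 for CS dissection, 2 for tortuous anatomy".

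Such a patient has no implant date, so the plan does not say when the calls or the last visit fall due. A late effusion, bleed or readmission would then come to light mainly if the patient or another physician volunteered it.

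Two results depend on this. Aim 5.4 is to confirm safety and feasibility, and failed attempts bear directly on both. The procedural MACE endpoint in Section 6.3 includes coronary sinus perforation and is counted over four months of follow-up, which for these patients has no stated start. The enrolment pause after the first six patients (Section 7.3) also waits for a one-month follow-up with the same unstated start.

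**Working it through.** **1. Does implant mean the procedure or a placed device?** The term is not defined. Calling Day 0 the implant day (Sections 11.3 and 11.8) allows the first reading. Usage elsewhere favours the second: the Table 2 footnotes describe patients with an attempt as not implanted, and Section 13.1 separates an attempted implant from an implant.

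**2. What is collected after a failed attempt?**

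| Type of event | Provision | Covered? |
|---|---|---|
| On the day of the attempt | Section 11.3; Section 13 opening (from consent) | Yes |
| Already known and unresolved | Sections 13.7 and 13.10 (followed until resolved or explained) | Yes |
| Hospitalisation for an adverse event, once known | Section 13.9 | Yes, as serious |
| New event after discharge | Section 13.10 requires active questioning, but only when there is a contact | No contact is scheduled |

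**3. Could such patients be screened out first?** Coronary sinus diameter and anatomy on angiogram, and mean right atrial pressure, are exclusions in Section 7.2. None appears in the lists in Sections 11.1 and 11.2 or in the schedule, so they may first be found at the implant procedure.

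**4. How often would an attempt fail?**

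Table 2 reproduced: COSIRA 50/52 = 96.15% (printed 96.2). REDUCER-I 204/211 = 96.68% (printed 96.6; it rounds to 96.7, which does not matter here).

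With n = 30 (Section 6.1) and non-implant rate p, expected failures = 30p and P(at least one) = 1 − (1 − p)^30.

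| Source | p | Expected in 30 | P(at least one) |
|---|---|---|---|
| COSIRA | 2/52 = 3.85% | 1.15 | 1 − (50/52)^30 = 0.69 |
| REDUCER-I overall | 7/211 = 3.32% | 1.00 | 1 − (204/211)^30 = 0.64 |
| Italian registry | 2/141 = 1.42% | 0.43 | 1 − (139/141)^30 = 0.35 |
| REDUCER-I, stopped for dissection | 2/211 = 0.95% | 0.28 | 1 − (209/211)^30 = 0.25 |

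The registry denominator is inferred: the text gives 98.6%, n = 139 and 2 failures, read as 139 + 2 = 141. Taking 139 as the total gives the same rounded results. REDUCER-I Arm 1 (7/161) lists the same number of failures in a smaller group and would give 1.30 expected and 0.74. The first-in-man series is left out because its one technical failure was a migration followed by a second device.

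Sensitivity: if the three REDUCER-I failures put down to tortuous or small anatomy were all excluded beforehand, p = 4/211, expected = 0.57 and P(at least one) = 1 − (207/211)^30 = 0.44. This lies inside the range above.

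**5. Analysis.** A patient without a device cannot complete every study procedure, because implantation is one of them. Section 12 states one analysis population and no separate one for safety. Read literally, it removes failed attempts from procedural MACE and feasibility.

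**The case against.** The strongest reply is that safety collection does not depend on a device being placed. Reporting starts at consent, the procedure day is covered, known events are followed to resolution, Section 13.9 captures hospitalisation whatever the implant status, and Section 13.10 asks for possibly related serious events even after the study period. Section 11.1 mentions a diary card between visits. The Project Summary says that procedural success will be recorded.

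Most of this stands. A reader might infer that all safety follow-up begins at a completed implant and that a failed-attempt patient is shut out of it. The documents do not support that. *Completed* is not their word, and they are silent about these patients rather than excluding them. Nor is Section 7.5 merely permissive, although it is limited to withdrawn subjects and does not name a failed implant as a withdrawal.

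The reply does not supply a contact. Resolution rules apply to events already known, a diary needs a visit at which it is reviewed, and the consent-based window ends at a post-implant visit. Recording procedural success is also not the same as analysing it under a completers-only rule.

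A second fair objection is that the 35–69% is the chance of a failed attempt, not of a missed late event. That is correct and limits what the figure shows.

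**Conclusion.** The point holds in a limited form. The follow-up period, the calls and the final visit are anchored to implant, and the plan states no Day 0 and no scheduled contact for a patient whose attempt fails. What is lost is active ascertainment of new events after the day of the attempt and, under Section 12 as written, the place of these patients in the safety and feasibility results. Immediate complications are captured.

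The scale is about one patient: 0.4 to 1.2 expected, with a 35–69% chance of at least one. This assumes that rates from earlier studies, largely in obstructive disease, apply to these 30 patients independently. The probability of an uncaptured late event is smaller, and the documents give no rate from which to compute it. In a 30-patient trial that sets out to confirm safety and feasibility, even one such patient is worth following, and the correction is cheap.

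**What to change.** - Reconcile the reporting windows in the opening of Section 13 and in Section 13.4, and define Day 0 in Sections 13.4 and 11.3–11.7 as the day of the attempted implantation.
- State that every patient with an attempt receives the existing Day 30, 60 and 90 calls and an adverse-event contact at Day 120, whether or not a device was placed. The sponsor should state which other Day 120 assessments apply when there is no device.
- Align Section 13.3 with Section 13.9 so that hospitalisation after an attempt counts.
- In Section 12, report procedural MACE and procedural success in all attempted patients rather than completers only. Without this, re-anchoring Day 0 would collect the data but leave these patients out of the results.

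The cost is protocol wording plus four contacts per failed attempt: 4 × 0.43 to 4 × 1.15, or about 2 to 5 contacts in the whole trial. The reported complication rate may come out slightly less favourable.
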